12.1.2. Vital Signs

Summary statistics of absolute values and percent change from Day 1 (Baseline) will be provided for BP (DBP and SBP), pulse rate, and RR. All values outside a predefined normal range will be flagged in the individual subject data listings.

12.1.3. Electrocardiogram

A 12-lead ECG will be recorded at Day 1 (Baseline) for those subjects that enroll greater than one week following completion of the previous study. All subjects will have an ECG at every study visit. Subjects who terminate early will also have an ECG at the End-of-Study visit.

12.1.4. Physical Examinations

Subjects who enroll in the study greater than one week following completion of the previous study will undergo a full physical examination at Day 1 (Baseline). All subjects in the study will undergo an updated physical examination at every study visit. A full physical examination will be conducted for all subjects who withdraw or are terminated from the study at an End-of-Study visit. Physical examination data will be included in data listings and reviewed for any clinically significant abnormalities.

12.1.5. Pharmacokinetic Analysis

Pharmacokinetic data will be summarized descriptively. If appropriate, data will be further stratified by age, gender, and/or other demographic variables. As appropriate, graphic summaries of the PK data will be prepared.

12.2 Efficacy Analysis

No formal statistical analysis is currently planned for the clinical rating scales (SAPS, UPDRS, CGI-I, CGI-S and Caregiver Burden Scale) recorded in this study; however, results for the safety population will be summarized with descriptive statistics at each study visit.

13. REGULATORY COMPLIANCE

13.1 Ethical Conduct of the Study

This study will be conducted in compliance with the protocol, the Declaration of Helsinki, ICH principles of Good Clinical Practice, and other applicable regulatory requirements.

13.2 Regulatory Approval

The Investigator at each site is responsible for obtaining IRB or EC approval for the final protocol, sponsor-approved ICF, and any advertisements to recruit subjects. Written approval of these documents must be obtained from the committee before any subject is enrolled at a center.

The Investigator is also responsible for the following interactions with the IRB or EC:

- Obtaining IRB or EC approval, as appropriate, for any protocol amendments and ICF revisions before implementing the changes;
- Providing the IRB or EC with any required information before or during the study;

- Submitting progress reports to the IRB or EC, as required, during the conduct of the study;
- Requesting re-review and approval of the study, as needed;
- Providing copies of all IRB or EC re-approvals and relevant communication to ACADIA and/or designee;
- Notifying the IRB or EC of all serious and unexpected AEs related to the investigational drug reported by ACADIA and/or designee, as required.

13.3 Subject Informed Consent

Prior to any study-related activities, an IRB- or EC-approved ICF (and HIPAA authorization where applicable) must be signed and dated by the subject and the caregiver. The Informed Consent must at a minimum include the elements of consent described in the ICH guidance on GCP and the U.S. Code of Federal Regulations 21CFR§50.25.

The Investigator's draft Informed Consent must be reviewed and approved by ACADIA and/or designee prior to IRB or EC submission. The Investigator's IRB or EC will review and approve the study protocol, ICF, HIPAA authorization and any other study document (s) according to local regulations. After approval by the IRB or EC committee, the following documentation will be sent to ACADIA or designee before the study commences:

- Confirmation of IRB or EC approval of the protocol
- Confirmation of IRB or EC approval of the ICF
- Confirmation of IRB or EC approval of the HIPAA authorization

In addition to the written ICF, it is the responsibility of the Investigator to ensure that each subject under consideration for inclusion into the study be given a verbal explanation of the nature, purpose, risks and requirements of the trial. Subjects must be given an adequate opportunity to ask the Investigator questions about any aspects of the trial. Once the subject has read the ICF, discussed it with the Investigator, and has agreed to participate, he/she will be asked to sign the informed consent (and HIPAA authorization, where applicable). The original, signed Informed Consent Form (ICF) and HIPAA authorization will remain at the site and copies will be given to the subject.

The subject's consent is confirmed by the dated signature of the subject and by the dated signature of the person conducting the informed consent discussions.

The subject's caregiver will also be asked to consent to participate in the study. The Investigator will use similar procedures to ensure that the caregiver understands the nature, purpose, risks and requirements of the trial. Caregivers must be given an adequate opportunity to ask the Investigator questions about any aspects of the trial prior to signing the ICF.

13.4 Subject Compensation for Adverse Effects on Health

ACADIA will adhere to any applicable local regulations regarding Clinical Trial Compensation Guidelines to subjects whose health is adversely affected by taking part in the study.

13.5 Protocol Amendments and Study Termination

Protocol amendments must be made only with the prior approval of ACADIA and documented approval/favorable opinion of the IRB or EC of an amendment, except where necessary to protect the safety, rights, or welfare of subjects. Agreement from the Investigator must be obtained for all protocol amendments and amendments to the Informed Consent document. The IRB or EC must be informed of all amendments and give approval for any amendments likely to affect the safety of the subjects or the conduct of the trial. The Investigator must send a copy of the approval letter from the IRB or EC to ACADIA and/or designee.

Both ACADIA and the Investigator reserve the right to terminate the study, according to the study contract. The Investigator should notify the IRB or EC in writing of the trial's completion or early termination and send a copy of the notification to ACADIA and/or designee.

13.6 Finance, Insurance and Indemnity

Arrangements for finance, insurance and indemnity are delineated in the Clinical Study Agreement and/or other separate agreements with the Investigator and/or Institution, as applicable.

13.7 Publication

All publication rights are delineated in the Clinical Study Agreement and/or other separate agreements with the Investigator and/or Institution, as applicable.

APPENDIX 1: PROHIBITED AND RESTRICTED CONCOMITANT MEDICATIONS

The following is an outline of the restrictions on concomitant medications. Any questions regarding prohibited and restricted concomitant medications should be discussed with the [REDACTED] Medical Monitor.

1. Antipsychotics are prohibited during the first month of the study, including clozapine, quetiapine, risperidone, olanzapine, ziprasidone. Addition of any antipsychotic after the first month of the study must be discussed with the Medical Monitor.
2. The following medications are prohibited and must have been discontinued no less than 30 days prior to Study Day 1: mianserin, mirtazepine, nefazodone, cyproheptadine, fluvoxamine, other investigational agents.
3. Centrally-acting anticholinergic medications are prohibited and must have been discontinued no less than 2 weeks prior to Study Day 1. These include, and are not limited to, benzotropine, biperiden, and trihexylphenidyl. Anticholinergic agents that act predominantly on the peripheral nervous system such as tolteradine or oxybutynin, are allowed.
4. Use of acetylcholinesterase inhibitors is allowed.
5. Medications that can prolong QT interval are prohibited. These include, and are not limited to the following:-
 - Antiarrhythmic drugs including quinidine, procainamide, disopyramide, ajmaline, encainide, flecainide, propafenone, amiodarone, sotalol, *d*-sotalol, bretylium, ibutilide, dofetilide, amakalant, semantilide
 - Anticonvulsants including felbamate, fosphenytoin
 - Antidepressants including amitriptyline, nortriptyline, imipramine, desipramine, clomipramine, maprotiline, doxepin
 - Antihistamines including diphenhydramine
 - Antimicrobial and antimalarial drugs including erythromycin, clarithromycin, ketoconazole, pentamidine, quinine, chloroquine, halofantrine
 - Antipsychotics including thioridazine, chlorpromazine, haloperidol, pimozide, ziprasidone, mesoridazine
 - Others including methadone, cocaine
6. Use of amantadine, which may cause QT prolongation, should be discussed with the medical monitor.

## LIST OF ABBREVIATIONS

ACADIA	ACADIA Pharmaceuticals Inc.
AE(s)	Adverse Event(s)
ATC	Anatomical/Therapeutic/Chemical
BMI	Body mass index
BP	Blood pressure
CFB	Change from Baseline
CGI-I	Clinical Global Impression – Improvement
CGI-S	Clinical Global Impression - Severity
DBP	Diastolic blood pressure
EC	Ethics Committee
ECG(s)	Electrocardiogram(s)
eCRF	Electronic case report form
HIPAA	Health Insurance Portability and Accountability Act
HR	Heart Rate
ICF	Informed Consent Form
MedDRA	Medical Dictionary for Regulatory Activities
mmHg	millimeters of mercury
msec	millisecond(s)
NDA	New drug application
NMSS	Non-Motor Symptoms Scale
PD	Parkinson's Disease
PDP	Parkinson's Disease psychosis
PE(s)	Physical Examination(s)
PK	Pharmacokinetic
PR	PR interval on an electrocardiogram tracing
QRS	QRS interval of electrocardiogram
QT	QT interval of electrocardiogram
QTc	QT interval of electrocardiogram; corrected for heart rate
QTcF	Corrected QT interval by the method of Fridericia
QTcB	Corrected QT interval by the method of Bazett

RUD-Lite	Resource Utilization in Dementia Lite
SAE(s)	Serious Adverse Event(s)
SAPS	Scale for the Assessment of Positive Symptoms
SAP-H+D	Combined SAPS-Hallucinations and Delusions Score
SBP	Systolic Blood Pressure
SD	Standard Deviation
SEM	Standard Error of the Mean
SOC	System Organ Class
SOP	Standard Operating Procedures
TEAE	Treatment-Emergent Adverse Event
UPDRS	Unified Parkinson's Disease Rating Scale
US	United States
WHO	World Health Organization

## DEFINITIONS

The following definitions are developed for the purpose of statistical analysis and data tabulation.

Adverse Event	An adverse event (AE) is any untoward medical occurrence or unintended change from the subject's pre-treatment condition, including inter-current illness, that occurs during the course of a clinical trial after treatment has started, whether considered related to study treatment or not. An AE can therefore be any unfavorable and unintended sign (including an abnormal laboratory finding, for example), symptom, or disease temporally associated with the use of a medicinal product, whether or not considered related to the medicinal product.
Baseline	Baseline is defined as the last available measurement taken prior to the first study drug administration in the ACP-103-015 study. If an ACP-103-015 baseline assessment was not scheduled to be performed, then the baseline value will be taken from the last available measurement in the core study.
Change from Baseline	For any given parameter at any given visit, the change from baseline (CFB) is defined as the parameter value for the given visit minus the Baseline value.
Descriptive Statistics	Number of subjects, mean, median, standard deviation, standard error of the mean, minimum and maximum for continuous measurements; number and percentage of subjects in each level of a categorical measurement.
Safety Analysis Set	The safety analysis set includes all enrolled subjects who receive any study drug in the ACP-103-015 study.
Safety Assessments	

• Adverse events

• Vital Signs

• Clinical Laboratory Tests

• Electrocardiogram (ECG)

• Physical Examinations

Baseline Procedures	Subjects enrolled within 1-week of completing the double-blind period a previous trial with pimavanserin are not required to undergo baseline procedures (except an update to the medical history and baseline RUD-Lite, Appendix A ). If they were enrolled after 1-week, all baseline procedures were required.

Serious Adverse Event	
A serious adverse event (SAE) is any AE with any of the following outcomes:
 

• Results in death;

• Is life-threatening (i.e., the subject was at risk of death at the time of the event; it does not refer to an event which hypothetically might have caused death if it were more severe);

• Requires inpatient hospitalization or prolongation of existing hospitalization;

• Results in persistent or significant disability/incapacity;

• Is a congenital anomaly or birth defect;

• Is an important medical event that may not be immediately life-threatening or result in death or hospitalization but based on appropriate medical judgment may jeopardize the subject or may require medical or surgical intervention to prevent one of the outcomes listed above. Examples of such events are intensive treatment in an emergency room or at home for allergic bronchospasm; blood dyscrasias or convulsions that do not result in hospitalization; or development of drug dependency or drug abuse.

Scheduled Visit	
A scheduled visit is any planned visit per the protocol schedule of events.

Study Day 1	
Study day 1 is defined as the date of first administration of study drug (pimavanserin) in the ACP-103-015 study.

Study Day n	
Study day n represents a visit or assessment that occurs n days relative to the start of study drug in the ACP-103-015 study, computed as: (date of visit – study day 1) + 1 if the date of visit occurs on or after date of first dose; otherwise computed as: (date of visit – study day 1). Note that there is no day 0.

Study Duration	
The duration of the open-label use of pimavanserin will be determined based on clinical evaluations but may continue for as long as this drug is considered to be well tolerated and efficacious, and until such time as pimavanserin is approved and commercially available

Treatment- Emergent Adverse Event      A treatment-emergent adverse event (TEAE) is defined as an adverse event started between first study dose date and 30 days after the last dose date in the ACP-103-015 study.

Treatment Group      All subjects will receive 40 mg of pimavanserin once per day (QD).

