### **5.13.3 Clinical Laboratory Data**

Observed clinical laboratory data and change from baseline values will be summarized by time period for hematology, chemistry and numeric urinalysis using the periods specified in Section 5.4.2 Table 2. For each laboratory parameter collected for each subject, within each time period, 2 different representations will be used for generating

the population summary statistics: the highest and lowest measurement from that subject during that particular time period. The highest or lowest measurement will capture the worst or the most extreme observed value (depending on the laboratory test, the highest or lowest or both can be concerning). In addition to each time period, for each laboratory parameter, the last, highest and lowest measurement collected for each subject during the entire study period will also be summarized.

For a subset of clinical laboratory parameters (red blood cell count, hemoglobin, white blood cell count, neutrophils, alkaline phosphatase, alanine aminotransferase, aspartate aminotransferase, bilirubin (total), gamma-glutamyl transferase, creatine phosphokinase, lactate dehydrogenase, blood urea nitrogen, creatinine, and uric acid) low [L], normal [N] or high [H] status will be determined based on the normal ranges provided by the testing laboratory.

The count and percentage of subjects with markedly abnormal post-baseline clinical laboratory parameters tabulated for all subjects and a subset of subjects with normal baseline will also be presented by time period and overall as defined in [Table 2](#) and for overall study period. The criteria for markedly abnormal laboratory values are provided in [Appendix B](#). For each laboratory parameter, within each specified time period and for overall study period, if a subject has at least 1 measurement meeting the marked abnormal criterion, this subject will be counted as having an incidence. The denominator for each laboratory parameter within each specified time period will be the total number of subjects with baseline and at least 1 post-baseline value within that particular time period.

Clinical laboratory data will be displayed in data listings with date and study day of collection. All units will be displayed according to the Système International (SI) conventions for units. Out-of-range values will be flagged in the data listings (i.e., 'L' or 'H').

The routine laboratory panel includes:

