### **5.13.4 Vital Signs and Weight**

#### **5.13.4.1 Vital Sign Parameters**

Vital signs are collected at every study visit. A summary of observed values and change from baseline by time period will be presented for orthostatic blood pressure (systolic and diastolic in mmHg) and pulse (beats per minute), measured supine (after 5 minute), and standing (after 1 minute), respiratory rate, oral temperature and weight. For each vital sign parameter collected for each subject, within each time period, 2 different representations will be used for generating the population summary statistics: the highest and lowest measurement. The highest or lowest measurement will capture the worst or the most extreme observed value. In addition to each time period, for each vital sign parameter, the last, highest and lowest measurement collected for each subject during the entire study period will also be summarized.

All observed and change from baseline vital sign values will be provided in a listing with date of collection, study day, and time period.

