#### **5.13.4.2 Orthostatic Hypotension**

Orthostatic hypotension is assessed each time vital signs are collected for pulse and blood pressure through the comparison of 5 minute supine results against 1 minute standing. The count and percentage of subjects experienced orthostatic hypotension as defined below will be summarized for each time period defined in [Section 5.4.2 Table 2](#) and for overall study period (at any timepoint postdose) for subjects for whom orthostatic hypotension was not present at baseline. If a subject has at least 1 measurement meeting the orthostatic hypotension criteria during a given time period, this subject will be counted as having an incidence for that time period. The denominator for percentages is the number of subjects with non-missing data at each visit.

Orthostatic hypotension occurs if:

- there is a decrease of  $\geq 20$  mmHg in systolic blood pressure (SBP)  
OR
- there is a decrease of  $\geq 15$  mmHg in diastolic blood pressure (DBP)  
OR
- there is an increase of  $\geq 20$  bpm in pulse rate (PR);

each measured from 5 minutes supine to 1 minute standing at the same visit.

An overall count and percentage of subjects experienced orthostatic hypotension based on findings from either AE records (i.e. where the preferred term = 'Orthostatic

hypotension') or vital signs (orthostatic changes in blood pressure and pulse) will also be presented. Data listing of blood pressure and pulse measurements for these subjects will also be presented.

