## APPENDIX B: Criteria for Markedly Abnormal Laboratory Values in SI (Système International) Units

Lab Analyte	Criteria
Chemistry	
Aspartate aminotransferase (AST)	≥ 3 x upper limit of normal
Alanine Aminotransferase (ALT)	≥ 3 x upper limit of normal
Alkaline Phosphatase	≥ 3 x upper limit of normal
Lactate Dehydrogenase (LDH)	≥ 3 x upper limit of normal
Blood Urea Nitrogen (BUN)	≥ 10.71 mmol/L
Creatinine	≥ 176.8 µmol/L
Uric Acid	
Males	≥ 619.5 µmol/L
Females	≥ 501.5 µmol/L
Bilirubin (total)	≥ 34.2 µmol/L
Creatine Kinase (CK)	≥ 3 x upper limit of normal
Hematology	
Hematocrit	
Males	≤ 0.37 and decrease of ≥ 0.03 from Baseline
Females	≤ 0.32 and decrease of ≥ 0.03 from Baseline
Hemoglobin	
Males	≤ 115 g/L
Females	≤ 95 g/L
White Blood Count (WBC)	≤ 2.8 x 10  /L or ≥ 16.0 x 10  /L
Eosinophils	≥ 10%
Neutrophils	Absolute Count < 1.5 x 10  /L
Platelet Count	≤ 100.0 x 10  /L or ≥ 700.0 x 10  /L

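### Lab, vital-sign, orthostatic and weight-change tables use a baseline that is on-drug or post-exposure for former pimavanserin subjects, with no prior-treatment split or pre-exposure view planned

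*SAP*

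**What the plan says.** The Definitions section of the SAP sets a single baseline for all parameters: "Baseline is defined as the last available measurement taken prior to the first study drug administration in the ACP-103-015 study". If no ACP-103-015 baseline assessment was scheduled, "then the baseline value will be taken from the last available measurement in the core study". This fallback applies to early entrants: "Subjects enrolled within 1-week of completing the double-blind period a previous trial with pimavanserin are not required to undergo baseline procedures" (medical history update and RUD-Lite excepted). Change from baseline is the visit value minus this baseline.

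Entry is allowed up to 28 days after blinded treatment (SAP 2.1). Prior treatment was placebo or pimavanserin 10, 20 or 40 mg (SAP 5.11.1).

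These summaries depend on that baseline:

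- SAP 5.13.3: "Observed clinical laboratory data and change from baseline values will be summarized by time period". Markedly abnormal labs are counted for all subjects, and "a subset of subjects with normal baseline will also be presented by time period and overall".
- SAP Appendix B, hematocrit in males: "≤ 0.37 and decrease of ≥ 0.03 from Baseline". The female criterion needs the same fall.
- SAP 5.13.4.1: "A summary of observed values and change from baseline by time period will be presented for orthostatic blood pressure" and the other vital signs.
- SAP 5.13.4.2: orthostatic incidence "for subjects for whom orthostatic hypotension was not present at baseline".
- SAP 5.13.4.3: weight increase or decrease of at least 7%.

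None of these sections plans a split by prior treatment or a pre-exposure baseline. The SAP does use both devices elsewhere. SAPS scores are summarized by prior treatment (5.11.1). ECG parameters are also summarized from a pre-PIM baseline, which is the core-study baseline for former pimavanserin subjects and the ACP-103-015 baseline for everyone else (5.13.5.1).

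**The concern.** Long-term safety and tolerability is the study's only objective (SAP 3.1). A former pimavanserin subject who enters within a week has an end-of-treatment value as baseline, and a later entrant has a recent post-exposure value with unknown carry-over. A former placebo subject's baseline is unexposed. A pooled table mixes the two kinds.

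For former pimavanserin subjects, any change that arose during the core study and persists at entry is subtracted from mean change. In the tables that exclude subjects with the finding at baseline, such a subject leaves the at-risk set. A reader of the pooled table cannot tell whether a small mean change means a small effect, or an effect already in place at entry for many subjects.

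**Working it through.** **No plan figure to reproduce.** The study is descriptive. The documents give neither the number of subjects by prior treatment nor any change during the core studies. All inputs below are assumptions that show direction and range.

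**1. Single-subject illustration.** A man has hematocrit 0.42 before any exposure, 0.39 at extension entry and 0.365 on study. The fall is 0.39 − 0.365 = 0.025 from the extension baseline, so he is not flagged. From pre-exposure it is 0.42 − 0.365 = 0.055, so he is flagged.

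**2. Mean change.** Let q be the share of subjects with an on-drug baseline and f the fraction of the drug effect already present at entry. The drug component of pooled mean change is multiplied by 1 − q·f:

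| f | q = 0.25 | q = 0.50 | q = 0.75 |
|---|---|---|---|
| 0 | 1.00 | 1.00 | 1.00 |
| 0.5 | 0.88 | 0.75 | 0.63 |
| 1 | 0.75 | 0.50 | 0.25 |

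**3. Weight change of 7% or more, either direction.** For one reading with mean change m and SD 5%, P(m) = [1 − Φ((7 − m)/5)] + Φ((−7 − m)/5). Assume a drug shift of +2%, f = 1, and non-drug drift d, the same for both kinds of baseline. Then m = 2 + d from a pre-exposure baseline and m = d from an on-drug baseline. At q = 0.5 the pooled figure is the average of the two.

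| Drift d | All pre-exposure | On-drug | Pooled |
|---|---|---|---|
| 0 | 15.87 + 3.59 = 19.5% | 8.08 + 8.08 = 16.2% | 17.8% |
| −1% | 11.51 + 5.48 = 17.0% | 5.48 + 11.51 = 17.0% | 17.0% |
| −2% | 8.08 + 8.08 = 16.2% | 3.59 + 15.87 = 19.5% | 17.8% |

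In each sum the first term is gains and the second is losses. The extension-baseline count falls, stays the same or rises according to drift. The two-sided total also hides movement in its parts. With no drift, pooled gains are (15.87 + 8.08)/2 = 12.0% against 15.9%, and pooled losses (3.59 + 8.08)/2 = 5.8% against 3.6%. At d = −1% the total does not move, but gains go from 11.5% to 8.5% and losses from 5.5% to 8.5%.

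**4. Orthostatic incidence, systolic criterion only.** This was simulated with 2,000,000 subjects per baseline type. Assumed: mean fall 5 mmHg off drug and 10 mmHg on drug, between- and within-subject SD 8 mmHg each, threshold 20 mmHg, subjects at or above threshold at baseline excluded, q = 0.5, f = 1. With one post-baseline reading, incidence is 15.6% from a pre-exposure baseline and 14.5% pooled. The SAP counts a subject with at least one qualifying reading, so the number of readings matters. With six readings the figures are about 46% and 44%.

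**The case against.** The strongest reply is that nothing is wrong. Extension entry is a natural baseline for describing change during an extension, and Protocol 12.1.2 specifies change from Day 1 for vital signs. That stands. A reader might infer that the SAP departs from the protocol or has made an error here; the documents do not support that.

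A reader might also infer from the ECG provision that a pre-exposure baseline was meant for the other parameters and left out. It does not show this. The protocol singles out QT through a QTcB entry limit and a ban on QT-prolonging drugs, which would explain special treatment for ECG alone. The ECG section shows only that a usable definition exists.

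Much also remains visible. Observed values, BMI limits, absolute lab criteria in all subjects and TEAEs by onset date do not use this baseline. For UPDRS no change from baseline is specified. These do not restore within-subject change or the at-risk denominators, but they limit the consequences. SAP 5.13.4.2 does not say whether the combined orthostatic count, from AE records or vital signs, keeps the baseline restriction, so whether it is affected is open.

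Finally, a pre-exposure baseline is not essential for every subject. For former placebo subjects the extension baseline already is one, so splitting the existing tables gives an undiluted view in that group. This stands and shapes the fix. In former pimavanserin subjects, change from a pre-exposure baseline spans the core study plus the extension, while the SAP's time periods start at the first ACP-103-015 dose. A footnote discloses that mixture but cannot remove it.

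**Conclusion.** The point holds as a gap in presentation. The listed lab, vital-sign, orthostatic and weight tables rest only on a baseline that is on-drug or recently post-exposure for former pimavanserin subjects. As pooled, they mix exposed and unexposed baselines with no planned way to separate them.

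Its size cannot be derived from the documents. The drug part of mean change is multiplied by 1 − q·f: no dilution if f = 0, half at q = 0.5 and f = 1. It is tempting to conclude that the threshold counts are understated. The documents do not support a general direction. In the assumed weight example the count goes from 19.5% to 17.8% with no drift, is unchanged at 17.0% with drift −1%, and goes from 16.2% to 17.8% with drift −2%. The choice f = 1 is also an extreme: former 10 and 20 mg subjects move to 40 mg, and later entrants may have partly lost the effect. In these examples the threshold tables move by about 2 points or less, and mean-change tables can move more.

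This is a cheap improvement of low-to-moderate priority.

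**What to change.** Keep the extension-baseline tables as planned, and add to SAP 5.13.3 and 5.13.4:

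1. Present lab change, markedly abnormal labs in subjects with normal baseline, the hematocrit criterion, vital-sign change, orthostatic hypotension not present at baseline, and weight change of 7% or more by core-study treatment (placebo, pimavanserin) as well. The former-placebo stratum is then a true pre-exposure view and needs no core-study data.
2. For former pimavanserin subjects, add supplementary versions of the same tables using the pre-PIM baseline of Section 5.13.5.1, not pooled with former placebo subjects. Footnote them: change spans the core study and the extension, whereas time periods count from the first ACP-103-015 dose.
3. Show weight increases and decreases of 7% or more separately.

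The cost is SAP wording, repeat table programs, more output, and retrieval of core-study baseline labs, vital signs and weight for item 2. No new visits or assessments are needed. The remaining weakness is that the former-pimavanserin tables in item 2 cover a longer elapsed time, which includes non-drug change in a progressive disease.
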